4.5.2. Risks of Potential Adverse Events with Study-Mandated Procedures

Blood will be drawn from study participants for safety and PK assessments, which imparts a small risk of venipuncture injury, infection, and hypotension. To reduce the risk of anemia, < 500 mL of blood will be drawn from any subject during the study (screening through last scheduled follow-up visit), and anemic subjects will not be allowed to enroll in the study or continue participation if they become anemic during the study. The total blood collected for this study for both PK and safety laboratory assessments will be approximately 300 mL.

Venipuncture may cause transient discomfort and may result in fainting. Fainting is usually transient and managed by having the subject lie down and elevate his/her legs. Bruising at the site of the venipuncture may occur but may be prevented or lessened by applying pressure to the site for several minutes. Venipuncture may also cause infection. The use of aseptic (sterile) technique will make infection at the site where blood will be drawn extremely unlikely.

4.5.3. Risks Associated with Infusions

Galidesivir at a concentration of 100 mg/mL will be diluted to a maximum concentration of 5 mg/mL using an LR solution. IV doses of galidesivir will be infused over 60 minutes via an IV catheter at a maximum rate of 8.33 mL/min. Nonclinical local tolerability studies in the rabbit showed that intra-arterial injection of 30 mg/kg and perivascular injection of 7.5 mg/animal caused severe erythema with no microscopic correlate. In Study BCX4430-101, there were no injection site changes such as erythema, edema, nodules, necrosis, etc., after IM injection. Taken together, these findings indicate that it is unlikely that extravasation of galidesivir-infused IV would cause injury; however, infusion sites will be closely monitored.

The pH of the diluted drug in LR that will be infused will be approximately 4.0 to 5.0 ([Alcami 2016](#)), which should buffer to a physiologic pH rapidly, making peripheral veins appropriate for infusion. General risks associated with IV infusions include pain, bruising, phlebitis, thrombosis of the cannulated vein, and leaking IV fluid into the tissues near the injection. Careful inspection of the site, including visualization of blood return at the catheter site and an infusion time of 60 minutes (ie, maximum rate of 8.33 mL/minute), will minimize this risk. There is a risk of infection; however, this is a small risk as aseptic technique will be employed to reduce this risk.

4.5.4. Known Potential Benefits

Apart from receiving a medical assessment during the screening process, there is no benefit to the subjects from taking part in this study. The development of galidesivir may be of benefit to the broader population as a potential therapeutic medical countermeasure for the treatment of MVD and other filovirus infections.

5. STUDY OBJECTIVES AND PURPOSE

5.1. Primary Objective

- To evaluate the safety and tolerability of SAD of galidesivir administered by IV infusion in healthy subjects

5.2. Secondary Objectives

- To characterize the plasma PK profile and urinary elimination of SAD of galidesivir administered by IV infusion in healthy subjects

6. ENDPOINTS

6.1. Primary Endpoints

- Safety and tolerability parameters including AEs and SAEs, laboratory abnormalities, vital signs, ECGs, ECHOs, cardiac telemetry, and PE findings

6.2. Secondary Endpoints

- Plasma and urine PK parameters for galidesivir
- Dose proportionality of galidesivir

7. INVESTIGATIONAL PLAN

7.1. Overall Study Design

This SAD study will evaluate the safety, tolerability, and PK of single doses of galidesivir vs. placebo administered as IV infusions in healthy subjects in up to four dose cohorts. A single dose of study drug will be administered to 8 subjects per cohort: 6 subjects will receive galidesivir IV, and 2 subjects will receive matching placebo.

The planned cohorts are as follows:

- Cohort 1, Regimen A: 5 mg/kg galidesivir or placebo, IV infusion × 1 dose
- Cohort 2, Regimen B: 10 mg/kg galidesivir or placebo, IV infusion × 1 dose
- Cohort 3, Regimen C: 15 mg/kg galidesivir or placebo, IV infusion × 1 dose
- Cohort 4, Regimen D: 20 mg/kg galidesivir or placebo, IV infusion × 1 dose

Study drug will be infused IV via a calibrated infusion pump over 60 minutes at a maximum rate of 8.33 mL/min.

As a safety precaution, on the first day of dosing in all cohorts, only 2 subjects will be dosed (to be referred to as sentinel subjects). The randomization schedule will be constructed such that 1 of the sentinel subjects dosed on the first day will be randomized to receive galidesivir and 1 will be randomized to receive placebo. The remainder of the cohort (5 subjects receiving galidesivir:

1 receiving placebo) will be dosed at least 2 days after the sentinels, contingent upon satisfactory results from safety assessments of the sentinel subjects.

Following a screening period to determine eligibility, subjects in each cohort will be admitted to the clinical research unit (CRU) on Day -1. Study eligibility will be confirmed upon admission to the CRU, and subjects will remain in the CRU overnight prior to dosing on Day 1. Following administration of the study drug on Day 1, subjects will remain in the CRU for 96 hours to enable collection of PK samples and safety and tolerability data. Subjects will be discharged from the CRU on Day 5, 96 hours after the start of the infusion. Subjects will return to the CRU for PK samples on Day 6 (+1 day), Day 8 (+1 day), and Day 14 (\pm 1 day). Subjects will return to the CRU for a final follow-up visit on Day 21 (+ 2 days). The study design is shown in [Figure 1](#).

In the event that there are any unresolved safety findings that are ongoing at Day 21, the subject will be followed at additional study visits until the findings are resolved or stabilized. If it is determined that the median half-life is longer than anticipated following IV infusion, or if after obtaining PK data through 96 hours, the AUC_{inf} estimate is $> 25\%$ of the AUC from time 0 to the last measurable concentration of drug (AUC_{last}), serial PK sampling may be extended beyond 96 hours in subsequent cohorts, or additional samples may be added in the intervening period between discharge from the CRU and the final follow-up visit (Day 21).

Safety and tolerability will be evaluated through assessments of AEs, laboratory analyses (clinical chemistry, hematology, coagulation, urinalysis, CK-MB, troponin), vital signs, ECGs, ECHOs, cardiac telemetry, and PEs at the time points indicated in the schedule of assessments. PK parameters will be analyzed from the plasma and urine samples collected at the time points indicated in the schedule of assessments ([Table 5](#)).

Enrollment of subjects in each sequential higher dose level cohort will occur only after completion of a clinical safety review of laboratory, AE, vital sign, ECG (12-lead and telemetry), and PE data for all subjects up through 96 hours post-dose and plasma PK data through 24 hours, by the Sponsor medical monitor, clinical pharmacologist, and principal investigator (PI) at a dose escalation review meeting. Rules for halting the escalation to the next dose will be followed as defined in Section [7.6.3.2](#).

Safety and PK data for each cohort will be submitted to the US Food and Drug Administration (FDA) after each cohort is complete. Escalation to the next planned dose may proceed as long as the halting rules are not triggered as defined in Section [7.6.3.2](#).

Figure 1: BCX4430-106 Study Design

Abbreviations: D = day; PK = pharmacokinetic.

Table 5: Schedule of Assessments

Assessment	Screening	In Clinic (CRU) Study Period							Return to CRU for PK Sample	Follow-up or Early Termination Visit
		Day -28 to -2	Day -1 (Admission)	Day 1 Baseline (Pre-dose)	Day 1 (Post dose)	Day 2	Day 3	Day 4	Day 5 (Discharge)	Day 6, Day 8, Day 14 ⁿ
Informed consent	X									
Inclusion/exclusion criteria	X	X								
Medical history	X	X								
Weight/height/BMI	X	X ^a								
Drugs of abuse screen/urine alcohol test/urine cotinine screen	X	X								
HIV/HCV/HBV serology	X									
Physical examination ^b	X	X	X	X	X	X	X	X		X
Concomitant medications	X	X	X	X	X	X	X	X	X	X
ECG	X ^c		X ^c	X ^d	X ^d	X ^d	X ^d	X ^d		X ^d
Cardiac telemetry			X ^e	X ^e						
ECHO ^f		X ^f					X ^f			

Assessment	Screening	In Clinic (CRU) Study Period							Return to CRU for PK Sample	Follow-up or Early Termination Visit
		Day -28 to -2	Day -1 (Admission)	Day 1 Baseline (Pre-dose)	Day 1 (Post dose)	Day 2	Day 3	Day 4		
Vital signs	X	X	X ^g	X ^g	X ^g	X	X	X		X
Pregnancy test ^h	X	X								X
FSH ⁱ	X									
Clinical chemistry/ hematology	X	X ^m		X	X	X	X	X		X
Urinalysis	X	X ^m			X	X	X	X		X
aPTT/PT	X	X ^m						X		X
Testosterone ^j		X ^m						X		X
Troponin I		X ^m						X		X
CK-MB		X ^m						X		X
Cystatin C and NGAL		X ^m						X		X
UACR	X	X ^m						X		X
Plasma for galidesivir PK analysis ^k			X ^k	X ^k	X	X	X	X	X	X
Urine for galidesivir PK analysis ^l			X	X	X	X	X	X		
AE assessment		X	X	X	X	X	X	X	X	X
Study drug dosing				X						

Abbreviations: AE = adverse event; aPTT = activated partial thromboplastin time; BMI = body mass index; CK-MB = creatine kinase-MB; CRU = clinical research unit; ECG = electrocardiogram; ECHO = echocardiogram; FSH = follicle-stimulating hormone; HBV = hepatitis B virus; HCV = hepatitis C virus; HIV = human immunodeficiency virus; NGAL = neutrophil gelatinase-associate lipocalin; PK = pharmacokinetic; PT = prothrombin time; UACR = urine albumin-to-creatinine ratio.

- a. Weight only.
- b. A physical examination consisting of the head and neck, skin, chest (lungs and heart), abdomen (gastrointestinal tract, liver, spleen and kidneys), back, musculoskeletal system, and neurologic system should be conducted at screening and on Day 5 prior to discharge. Breast and genitourinary system do not require examination unless the potential subject indicates a complaint or comorbidity that could result in exclusion. All other physical exams will be symptom directed. The site of infusion should be checked for any changes in skin.
- c. Three (3) serial ECGs will be performed at screening and baseline 1–3 minutes apart. Pre-dose ECG should be collected within \leq 2 hours of the first dose.
- d. 12-lead ECGs will be conducted on Day 1 at 2 and 4 hours post dose (post start of the infusion) and on Day 2 at 24 hours post dose (post start of the infusion). An acceptable window is \pm 10 minutes from the nominal time point. All subsequent ECGs are daily.
- e. Cardiac telemetry will be initiated \geq 2 hours prior to administration of the dose and will continue for 24 hours after the infusion is started. Subjects may be disconnected for bathroom, hygiene needs, and for 20-minute periods 3 times a day for meals. In addition, subjects may be disconnected for 10 minutes every 2 hours while awake for mild physical exercise such as walking or calf exercises.
- f. The ECHO may be performed at any time from screening to Day -2 for eligibility determination. An ECHO should also be performed on Day 4. An acceptable window for the Day 4 ECHO is up until Day 5 discharge.
- g. Vital signs (except temperature) will be obtained pre-dose (within 2 hours of dosing) 1, 2, 4, and 8 hours post dose (post start of the infusion) on Day 1, at 24 hours post dose on Day 2 and once per day where indicated. Oral temperature will be obtained at 8 hours post dose on Day 1 and at 24 hours post dose on Day 2. Subjects should be rested for 10 minutes in the supine position prior to vital sign measurements. All times are from the start of the infusion.
- h. A serum pregnancy test will be administered at screening to all women; all other pregnancy tests performed during the study may be urine pregnancy tests.
- i. An FSH level will be measured in women who report that they have been postmenopausal \leq 2 years.
- j. Free testosterone will be measured in male subjects.
- k. Plasma for PK galidesivir analysis will be collected pre-dose, 30 min (halfway through the infusion), 1 h (end of the infusion), 1.25 h, 1.5 h, 2 h, 3 h, 4 h, 6 h, 8 h, 10 h, 12 h, 16 h, 24 h, 36 h, 48 h, 60 h, 72 h, and 96 h following the start of the infusion. The pre-dose PK sample must be collected within \leq 1 hour of the dose. Assessment windows around each PK draw will be \pm 2 minutes for sampling times up to 2-hour post dose and from 2-hour post dose onward, \pm 10 minutes while subject is confined in the unit. All sample times are from the start of the infusion.
- l. For the analysis of urinary excretion of galidesivir, an aliquot of urine will be collected pre-dose (0 hour) and all urine will be collected for the following post dose intervals: 0–12 hours, 12–24 hours, 24–48 hours, 48–72 hours, and 72–96 hours. All sample times are from the start of the infusion.
- m. Baseline for study post dose comparisons. NGAL, cystatin C, UACR, testosterone, troponin I, and CK-MB can be collected on Day -1 or Day 1 (pre-dose). Subjects will return to the CRU to have a plasma PK sample collected on Day 6 (+1), Day 8 (+1), and Day 14 (\pm 1). This visit is intended to be a short visit (approximately 1-2 hours) and can take place at any time during the specified window. A plasma PK sample will also be collected at the follow-up visit on Day 21.

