As a safety precaution, on the first day of dosing in all cohorts, only 2 subjects will be dosed (to be referred to as sentinel subjects). The randomization schedule will be constructed such that 1 of the sentinel subjects dosed on the first day will be randomized to receive galidesivir and 1 will be randomized to receive placebo. After review of the safety data from the 24-hour post-dose period for the sentinel subjects, which includes review of any AEs, any abnormalities in the bedside ECGs, safety laboratory assessments and vital signs as described in Section 7.6.1, the remainder of the cohort (5 subjects randomized to galidesivir; 1 randomized to placebo) will be dosed at least 2 days after the sentinel subjects.

Following a 28-day screening period to determine eligibility, subjects in each cohort will be admitted to the Clinical Research Unit (CRU) on Day -1. Study eligibility will be confirmed upon admission to the CRU, and subjects will remain in the CRU overnight prior to dosing on Day 1. Following administration of study drug on Day 1, subjects will remain in the CRU for 96 hours to enable collection of PK samples and safety and tolerability data. Subjects will be discharged from the CRU on Day 5, 96 hours after the start of the infusion. Subjects will return to the CRU for a brief visit (approximately 1 to 2 hours) for PK sample collection on Day 6 (+ 1 day), Day 8 (+ 1 day), and Day 14 (\pm 1 day). Subjects will return to the CRU for a final follow-up visit on Day 21 (+ 2 days). In the event that there are any unresolved safety findings that are ongoing at Day 21, the subject will be followed at additional study visits until the findings are resolved or stabilized. If it is determined that the median half-life is longer than anticipated following IV infusion, or if after obtaining PK data through 96 hours, the area under the concentration-time curve (AUC) extrapolated to infinity (AUC_{inf}) estimate is $> 25\%$ of the AUC from time 0 to the last measurable concentration of drug (AUC_{last}), serial PK sampling may be extended beyond 96 hours in subsequent cohorts, or additional samples may be added in the intervening period between discharge from the CRU and the final follow-up visit at Day 21 (+2 days).

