^c Data from 1 subject were excluded from summary statistics because R^2 was < 7

^d Data from 1 subject were excluded from summary statistics because the extrapolated portion of AUC was \geq 25%

^e Data from 2 subjects were excluded from summary statistics because the extrapolated portion of AUC was \geq 25%

^f Data from 3 subjects were excluded from summary statistics because the extrapolated portion of AUC was \geq 25%

Note: Study medication was administered IM.

PK parameters for Part 3 are presented in [Table 4](#). On Days 1 and 7, over the multiple dose range of 2.5 to 10.0 mg/kg, AUC from time 0 to the end of the dosing interval (AUC_{tau}) demonstrated dose proportionality; the increase in C_{max} with dose was modestly greater than dose proportional with the power model and consistent with dose proportionality with the ANOVA model.

Overall, there was an approximately 1.5-fold increase in exposure (AUC) with repeat dosing over 7 days. Assessment of trough concentrations of galidesivir suggested that steady state had not been achieved by Day 7.

Table 4: Study BCX4430-101 Part 3: Summary of Select Plasma Pharmacokinetic Parameters Following 7-Day, Multiple Ascending Intramuscular Galidesivir Regimens (Days 1 and 7)

PK Parameter	2.5 mg/kg Galidesivir N = 7		5.0 mg/kg Galidesivir N = 8		10.0 mg/kg Galidesivir N = 8	
	Day 1	Day 7	Day 1	Day 7	Day 1	Day 7
C _{max} (ng/mL) ^a	1820 (18.7) n = 7	2390 (39.0) n = 7	6840 (12.6) n = 8	6900 (17.4) n = 8	11400 (25.3) n = 8	17500 (83.3) n = 7
T _{max} (h) ^b	0.25 (0.08, 0.50) n = 7	0.25 (0.10, 0.52) n = 7	0.25 (0.25, 0.50) n = 8	0.25 (0.08, 0.25) n = 8	0.25 (0.25, 0.25) n = 8	0.25 (0.08, 0.50) n = 7
C _{tau} (ng/ mL) ^a	33.6 (23.9) n = 7	138 (19.1) n = 7	68.4 (15.9) n = 8	280 (17.8) n = 8	134 (15.7) n = 8	494 (16.6) n = 7
AUC _t (ng.h/mL) ^a	4830 (16.9) n = 7	15100 (16.1) n = 7	12100 (11.6) n = 8	32500 (11.5) n = 8	21600 (10.1) n = 8	62100 (13.9) n = 7
AUC _{tau} (ng.h/mL) ^a	4830 (17.0) n = 7	7620 (17.0) n = 7	12100 (11.6) n = 8	17600 (10.3) n = 8	21700 (10.1) n = 8	34500 (13.6) n = 7
t _{1/2} (h) ^a	NR	104 (15.9) n = 7	NR	85.7 (17.3) n = 8	NR	113 (26.4) n = 7

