12.3.1.4. Pharmacokinetic Analysis

Concentrations of galidesivir will be determined by validated plasma and urine assays and will be summarized by treatment and displayed in figures. Plasma PK parameters for each subject will be estimated over the sampling interval using noncompartmental analysis (Phoenix WinNonlin Version 7.0 or higher, Certara) and summarized by treatment group using descriptive statistics. The amount and percentage of galidesivir excreted in the urine will be assessed at all doses. If possible, data will be summarized by cohort and dose proportionality assessed.

The PK parameters that will be estimated for galidesivir are listed in [Table 9](#). Additional analyses may be conducted as appropriate.

Table 9: Pharmacokinetic Parameters

Pharmacokinetic Parameter	Definition
AUC _{inf}	Area under the concentration versus time curve extrapolated to infinite time, calculated as AUC _{last} + (C _{last} /λ _z)
AUC _t	Area under the concentration versus time curve from time zero to time “t”; may be denoted as AUC _{last} if the “t” is the last timepoint with a measurable concentration
% AUC _{exp}	Percentage of AUC extrapolated between AUC _{last} and AUC _{inf}
C _{last}	Last measurable concentration of drug
C _{max}	Maximum observed concentration of drug
t _{1/2}	Estimate of the terminal elimination half-life of the drug
CL	CL = Dose/AUC where “Dose” is the dose of the drug and AUC = AUC _{inf}
λ _z	Terminal elimination rate constant, estimate by linear regression of the terminal elimination phase of the concentration of drug versus time curve
V _z	Volume of distribution of the drug
T _{max}	Time to C _{max}
CL _r	Renal clearance of unchanged drug in a specific interval (CL _r [interval]) or cumulatively over all collection intervals
% Dose _{excreted}	Percentage of given dose excreted in the urine as unchanged drug

In all derivations of PK parameters, zero will be substituted for concentrations below the quantitation limit (BQL) of the assay. Samples that are BQL, but are between two samples with detectable concentrations will be excluded from PK analysis.

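### The AUC trigger for extending PK sampling compares total AUCinf with 25% of AUClast, so it is met by every estimable profile and cannot judge whether 96-hour sampling is adequate

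*Protocol*

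**What the plan says.** Protocol Section 7.1 gives two conditions joined by *or*. The first is "If it is determined that the median half-life is longer than anticipated following IV infusion", with no number attached. The second is that, once data through 96 hours are in hand, "the AUC_{inf} estimate is $> 25\%$ of the AUC from time 0 to the last measurable concentration of drug". The Synopsis makes the same comparison: "extrapolated to infinity (AUC_{inf}) estimate is $> 25\%$ of the AUC from time 0 to the last measurable concentration of drug". If either condition holds, "serial PK sampling may be extended beyond 96 hours in subsequent cohorts", or samples may be added between discharge and the Day 21 visit.

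Table 9 (Protocol Section 12.3.1.4) defines AUCinf as "Area under the concentration versus time curve extrapolated to infinite time, calculated as" AUClast + (Clast/λz). It lists the extrapolated share as a separate parameter, %AUCexp: "Percentage of AUC extrapolated between" AUClast and AUCinf. The trigger does not use that parameter.

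In the summary of Study BCX4430-101, the footnotes to Table 3 apply a 25% limit to the extrapolated part. An example is "Data from 3 subjects were excluded from summary statistics because the extrapolated portion of AUC was" 25% or more. They do not name the denominator.

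The SAP does not restate the trigger. Its Section 16.1.1 repeats the Table 9 definitions and keeps the extrapolated percentage for listings only.

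**The concern.** A rule for lengthening sampling should ask how much of the total area rests on extrapolation. This one has the total area where the extrapolated part belongs, so its answer is fixed before any data are seen.

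The question is a real one for this drug. AUCinf is one of three dose-proportionality parameters and the denominator of CL. In Study BCX4430-101 a sizeable minority of subjects had 25% or more of their AUC extrapolated. The sentence is where the plan puts a number on adequate 96-hour sampling, and the number does no work.

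**Working it through.** **1. Algebra.** From Table 9, AUCinf/AUClast = 1 + (Clast/λz)/AUClast. All three quantities are positive, so the ratio cannot fall below 100%. The threshold is 25%. Without an estimable λz there is no AUCinf, so whenever the condition can be evaluated it is true.

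**2. The documents' own pairs.** Inputs are geometric means (ng·h/mL) from Protocol Table 3 (Study BCX4430-101, IM, with AUCt taken as AUClast) and from the Cohort 2 PK summary supplied with the SAP.

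| Dose | AUClast | AUCinf | AUCinf/AUClast | Condition as written |
|---|---|---|---|---|
| 0.3 mg/kg IM | 518 | 527 | 101.7% | met |
| 0.75 mg/kg IM | 1,340 | 1,650 | 123.1% | met |
| 1.8 mg/kg IM | 3,890 | 4,770 | 122.6% | met |
| 4.0 mg/kg IM | 10,100 | 11,900 | 117.8% | met |
| 7.0 mg/kg IM | 18,900 | 24,000 | 127.0% | met |
| 10 mg/kg IM | 27,100 | 32,900 | 121.4% | met |
| 10 mg/kg IV (Cohort 2) | 30,200 | 32,400 | 107.3% | met |

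At most IM doses the two parameters have different n, so these rows only illustrate step 1.

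**3. The extrapolated share does discriminate.** The Table 3 footnotes flag 1, 2, 3, 3, 0 and 2 subjects across the six doses at 25% or more. That is 11 of 36: some profiles fail and most pass.

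**4. Two possible repairs.** Let E = AUCinf − AUClast. If E/AUClast = x, then E/AUCinf = x/(1 + x).

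- E > 25% of AUClast is the same as E > 0.25/1.25 = 20% of AUCinf.
- E > 25% of AUCinf is the same as E > 0.25/0.75 = 33.3% of AUClast.

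They can disagree. At 7 mg/kg (n = 6 for both parameters) E = 24,000 − 18,900 = 5,100. Then 5,100/18,900 = 27.0% of AUClast, which triggers, and 5,100/24,000 = 21.2% of AUCinf, which does not.

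**5. Which denominator Study BCX4430-101 used.** With the same six subjects, the ratio of geometric means is the geometric mean of the individual ratios. A value of 1.27 therefore needs at least one subject with E of at least 27% of AUClast. None was excluded at that dose under the 25% limit, which suggests that the limit was applied to AUCinf. Rounding does not change this: 23,950/18,950 = 1.264, still above 1.25.

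**6. What Cohort 2 says about 96 hours.** The summary gives AUC0-24 of 20,400, AUCinf of 32,400 and a half-life of 89.1 h. Assume mono-exponential decline after 24 h.

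- Area beyond 24 h: 32,400 − 20,400 = 12,000.
- Decline from 24 to 96 h: exp(−0.693 × 72/89.1) = exp(−0.56) = 0.571.
- Area beyond 96 h: 12,000 × 0.571 ≈ 6,850, leaving about 25,550 through 96 h.
- Share: 6,850/32,400 ≈ 21% of AUCinf, or 6,850/25,550 ≈ 27% of AUClast.

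Faster decline soon after 24 h would lower both shares.

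**The case against.** The strongest reply is that little depends on the sentence. The action is permissive. Protocol Section 11.2.1 already lets PK sampling times be changed in the light of early cohorts, with no threshold. Every subject is sampled on Days 6, 8, 14 and 21. Day 21 is about 480 h, or 480/89.1 ≈ 5.4 half-lives at the Cohort 2 value. The trigger is not among the dose-escalation criteria, and no endpoint or analysis population refers to it. A pharmacologist would also see that a phrase for the extrapolated part has dropped out, because that quantity is defined in Table 9 and tabulated for Cohort 2.

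All of this stands, and it limits the consequence. It does not make the condition correct. The half-life condition cannot rescue it either, since one always-true limb of an *or* makes the whole always true. Nor does recognising the intent settle the rule, because two readings remain and they can give different answers.

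A reader might go further and cite Cohort 2 as a case where the trigger fired although extrapolation was only 11.1% (as stated) or 6.8% (2,200/32,400, from the geometric means). The documents do not support that. The trigger concerns data through 96 hours, and the Cohort 2 summary does not say that its AUC0-last stops there. The rough tail above puts the 96-hour share near either corrected cut-off, not well below it. The 6.8% is also a ratio of means that may rest on different subjects: the summary leaves one subject's half-life and clearance out of the means if that subject received active drug.

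**Conclusion.** The point holds as a wording error in an operative threshold. As written, the AUC condition is met in 100% of profiles with an estimable λz. This follows from the Table 9 definition alone and needs no assumption about the drug.

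The consequence is small. A reader might infer that the wording forces extra sampling, or that it puts dose escalation or the PK results at risk. Neither follows, given the optional action, the separate permission in Section 11.2.1 and the samples scheduled to Day 21. What is lost is a usable test of whether 96 hours is enough.

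Two statements rest on more than the definition. That Study BCX4430-101 used AUCinf as denominator is an inference from the 7 mg/kg row; it assumes that AUCt there is AUClast and that the exclusion rule was applied consistently. The Cohort 2 shares of about 21% and 27% assume mono-exponential decline after 24 h and coherent geometric means. They show only that the reported 11.1% and 6.8% cannot stand in for 96-hour extrapolation.

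**What to change.** In Protocol Section 7.1 and the Synopsis, restate the AUC condition on the extrapolated portion, AUCinf − AUClast, with both areas computed from data through 96 hours. The sponsor should choose the denominator and name it:

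- **AUCinf:** %AUCexp above 25%. This appears to match Study BCX4430-101.
- **AUClast:** extrapolated portion above 25% of AUClast, equal to 20% of AUCinf. This keeps the denominator that the protocol names and triggers earlier.

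In the same sentence, say whether the condition applies to the cohort median or to a stated number of subjects. The cost is one sentence in two places, with no change to design, sample size or scheduled visits.
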